#### I. Revisions in response to RRA for cabozantinib from [name] ([contact]), dated 29 MAR 2019

#	Section	Description of Change
1.	7.1	
The CAEPR Version 2.3, October 4, 2016 was updated to CAEPR Version 2.4, December 17, 2018.
 

• The SPEER grades have been updated.

• The section below utilizes CTCAE 5.0 language unless otherwise noted.

• Added New Risk:

• Also Reported on XL184 Trials But With Insufficient Evidence for Attribution: Anal mucositis; Atrioventricular block complete; Budd-Chiari syndrome; Cardiac disorders - Other (hypokinetic cardiomyopathy); Chest wall pain; Death NOS; Dysphasia; Ejection fraction decreased; Gastroesophageal reflux disease; Gastrointestinal pain; General disorders and administration site conditions - Other (general physical health deterioration); Gingival pain; Hepatobiliary disorders - Other (hepatic thrombus); Hepatobiliary disorders - Other (hepatorenal syndrome); Hoarseness; Hypothermia; Pain of skin; Pelvic pain; Periodontal disease; Scrotal pain; Sinus bradycardia; Sinus tachycardia; Skin hypopigmentation; Sudden death NOS; Thyroid stimulating hormone increased; Toothache; Vaginal inflammation; Vaginal perforation

• Increase in Risk Attribution:

• Changed to Less Likely from Also Reported on XL184 Trials But With Insufficient Evidence for Attribution: Generalized muscle weakness; Hematuria; Hypophosphatemia

• Changed to Rare but Serious from Also Reported on XL184 Trials But With Insufficient Evidence for Attribution: Intracranial hemorrhage; Ischemia cerebrovascular; Stroke; Transient ischemic attacks

• Decrease in Risk Attribution:

• Changed to Less Likely from Likely: Voice alteration

• Changed to Also Reported on XL184 Trials But With Insufficient Evidence for Attribution from Less Likely: Acute kidney injury

• Provided Further Clarification:

#	Section	Description of Change
		
 
• Footnote #8 has been updated to “Respiratory hemorrhage includes Bronchopulmonary hemorrhage, Epistaxis, Hemoptysis, Laryngeal hemorrhage, Mediastinal hemorrhage, Pharyngeal hemorrhage, and Pleural hemorrhage under the RESPIRATORY, THORACIC AND MEDIASTINAL DISORDERS SOC” from “Respiratory hemorrhage includes Bronchopulmonary hemorrhage, Epistaxis, Laryngeal hemorrhage, Mediastinal hemorrhage, Pharyngeal hemorrhage, and Pleural hemorrhage under the RESPIRATORY, THORACIC AND MEDIASTINAL DISORDERS SOC.”
 
• Musculoskeletal and connective tissue disorder - Other (muscle spasm) (CTCAE 4.0 language) is now reported as Muscle cramp.
 
• Skin and subcutaneous tissue disorders - Other (hair color changes) (CTCAE 4.0 language) is now reported as Hair color changes.
 
• Acute coronary syndrome is now reported as part of Chest pain - cardiac.
 
• Endocrine disorders - Other (hypopituitarism) (CTCAE 4.0 language) is now reported as Hypopituitarism.
 
• Gastrointestinal disorders - Other (gastroenteritis) is now reported as part of Infection.
 
• Gastrointestinal disorders - Other (anal fissure) (CTCAE 4.0 language) is now reported as Anal fissure.
 
• Investigations - Other (blood lactate dehydrogenase increased) (CTCAE 4.0 language) is now reported as Blood lactate dehydrogenase increased.
 
• Investigations - Other (eosinophil count increased) (CTCAE 4.0 language) is now reported as Eosinophilia under the BLOOD AND LYMPHATIC SYSTEM DISORDERS SOC.
 
• Investigations - Other (glucose urine present) (CTCAE 4.0 language) is now reported as Glucosuria under the RENAL AND URINARY DISORDERS SOC.
 
• Musculoskeletal and connective tissue disorder - Other (osteonecrosis) (CTCAE 4.0 language) is now reported as Osteonecrosis.
 
• Musculoskeletal and connective tissue disorder - Other (rhabdomyolysis) (CTCAE 4.0 language) is now reported as Rhabdomyolysis.
 
• Neoplasms benign, malignant and unspecified (incl cysts and polyps) - Other (tumor hemorrhage) (CTCAE 4.0 language) is now reported as Tumor hemorrhage.
 
• Nervous system disorders - Other (cerebral hematoma) is now reported as part of Hematoma under the VASCULAR DISORDERS SOC.
 
• Nervous system disorders - Other (spinal cord compression) (CTCAE 4.0 language) is now reported as Spinal cord compression.
 
• Renal and urinary disorders - Other (azotemia) is now part of Acute kidney injury.
 
• Respiratory, thoracic and mediastinal disorders - Other (oropharyngeal pain) (CTCAE 4.0 language) is now reported as Oropharyngeal pain.
 
• Skin and subcutaneous tissue disorders - Other (splinter hemorrhage) is now reported as Nail changes.
 

2.	ICD, Risks Section	The text preceding the Risk Table in risk list section was updated to include the wording from the new NCI Consent Form Template (version: November 27, 2018).
	ICD, Risk Table	The Risk Profile was updated. The Risk Profile was updated to align with CAEPR Version 2.4, December 17, 2018.

#	Section	Description of Change
		
 
• Increase in Risk Attribution: 
 
• Changed to Occasional from Also Reported on XL184 Trials But With Insufficient Evidence for Attribution (i.e., added to the Risk Profile): Muscle weakness; Blood in urine
 
• Changed to Rare from Also Reported on XL184 Trials But With Insufficient Evidence for Attribution (i.e., added to the Risk Profile): Bleeding in the brain which may cause confusion; Stroke which may cause paralysis, weakness
 
 
 
• Decrease in Risk Attribution: 
 
• Changed to Occasional from Common: Changes in voice
 
• Changed to Also Reported on XL184 Trials But With Insufficient Evidence for Attribution from Occasional (i.e., removed from the Risk Profile): Kidney damage which may require dialysis
 
 
 
• Provided Further Clarification: 
 
• High blood pressure which may cause blurred vision (under Common) is now reported as High blood pressure which may cause headaches, dizziness, blurred vision (under Common).
 
• Muscle spasms (under Occasional) is now reported as Pain (under Occasional).
 
• Internal bleeding which may cause coughing up blood, black tarry stool or blood in vomit (under Occasional) is now reported as Internal bleeding which may cause black tarry stool, blood in vomit, coughing up blood, or blood in urine (under Occasional).
 
• Sores in mouth which may cause difficulty swallowing (under Occasional) is now reported as Sores in the mouth which may cause difficulty swallowing (under Occasional).
 
 
 

## II. Administrative and Editorial Changes

#	Section	Description of Change
3.	Global	The protocol and ICD version number has been updated from 10.0 to 11.0 and the date has been updated from 27MAR2018 to 18APR2019.
4.	Protocol Roster	The Protocol Statistician was updated to [name] as [name] is no longer with the AMC Statistical Center.

## PROTOCOL SYNOPSIS

**Title:** Phase I Trial of Cabozantinib (XL184) for Advanced Solid Tumors in Persons with HIV Infection

**Phase of Study:** Phase I

**Participating Institutions:** This protocol will be open to all AMC member sites.

**Accrual Target:** 16 to 42 participants

**Population:** Participants with incurable recurrent or metastatic solid tumors and HIV infection.

**Regimen:** This is a phase I, dose escalation study of cabozantinib (XL184) for advanced solid tumors in persons with HIV infection. Cabozantinib will be administered orally as a once daily dose continuously for 28-day cycles, according to the Protocol Schema. Participants will be stratified into three groups based on which HAART therapy they are receiving. The first group (**Stratum A**) will be participants on either ritonavir or cobicistat (potent CYP3A4 inhibitor)-containing antiretroviral therapy. Since a potential interaction leading to higher drug levels of cabozantinib in participants on ritonavir or cobicistat is expected, participants will be dose escalated, starting at ~33% of the standard dose (60 mg), using a classic 3 + 3 phase I clinical trial design. Dose increases will be in 20 mg increments to a maximum of 60 mg/day. The second group (**Stratum B**) will be participants being treated with either efavirenz or etravirine-containing regimens, in whom CYP3A4 induction may lead to lower levels of the study drug. These participants will be treated at the standard dose of cabozantinib, then dose escalated by 20 mg/cohort to a maximum of 100 mg/day in a 3 + 3 design. The third group (**Stratum C**) will include participants taking antiretrovirals not specified in Stratum A or B, or who are not receiving active antiretroviral therapy. These participants will be treated at the standard dose of 60 mg/day; no dose escalation is planned in this Stratum.

In this trial, a dose-limiting toxicity (DLT) will be defined as any cabozantinib-related grade 3 or 4 non-hematologic toxicity during the first cycle of therapy, including grade 3 nausea and/or vomiting and grade 3 diarrhea despite prophylaxis and/or treatment or any of the following grade 4 hematologic toxicities during the first cycle of therapy: thrombocytopenia, neutropenia of more than 5 days duration, and neutropenia of any duration with fever or documented infection; additionally, treatment delay of 14 days or greater during Cycle 1 due to unresolved toxicity or any

dose reduction required during Cycle 1 due to a cabozantinib-related adverse event will be considered a DLT.

All participating participants will have pharmacokinetic sampling studies. Response evaluation by RECIST 1.1 will be obtained on all participants at baseline and at 8 week intervals.

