## PROTOCOL SCHEMA

Dose Level	Dose Escalation Schedule		
	Dose of Cabozantinib (XL184)*		
	Stratum A ART Regimens Including Drugs that Inhibit CYP3A4 A (mg/day)	Stratum B ART Regimens Including Drugs that Induce CYP3A4 B (mg/day)	Stratum C All Other ART Regimens C (mg/day)
Level -2	-	20	20
Level -1	20 mg every other day	40	40
Level 1	20	60	60
Level 2	40	100	-
Level 3	60	-	-

**\* Cabozantinib (XL184): must be taken on an empty stomach. Participants must be instructed not to eat for at least 2 hours before and at least 1 hour after taking cabozantinib. Participants should be instructed to take their cabozantinib dose at approximately the same time every day. If a participant misses a dose, the dose may be taken later only if it is within 12 hours of when the missed dose should have been taken. The missed dose should not be made up if it is within 12 hours of the next scheduled dose.**

A Stratum A: Participants taking either ritonavir-boosted or cobicistat-boosted ART regimens

B Stratum B: Participants taking either efavirenz or etravirine-based ART regimens.

C Stratum C: Participants taking any antiretrovirals not specified in Stratum A or B as of November 30, 2012, and participants who are not taking an ART regimen.

**Note: If an antiretroviral is FDA-approved after November 30, 2012, consult the Study Pharmacologist for Stratum designation).**

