## 5.0 TREATMENT PLAN

### 5.1 Agent Administration

Treatment will be administered on an outpatient basis. Reported adverse events and potential risks are described in [Section 7.0](#). Appropriate dose modifications are described in [Section 6.0](#). No investigational or commercial agents or therapies other than those described below may be administered with the intent to treat the participant's malignancy.

Cabozantinib will be administered orally as once daily doses continuously over 28 day cycles in each of three treatment strata in participant cohorts as detailed in the table below. The starting dose in each treatment Stratum will be Dose Level 1. Dose escalation will proceed in participant cohorts within each Stratum according to the scheme described in [Section 5.2](#).

**NOTES: The participant will be requested to maintain a medication diary of each dose of medication. The medication diary will be returned to clinic staff at the end of each course.**

**The site will be required to document study agent return by participant in source documents. Non-compliance with study agent administration should be noted at the time of diary collection and the participant should be instructed again regarding dosing instructions.**

**Missed cabozantinib doses will NOT be made up. Participants who have missed a dose should wait until the next scheduled dose to resume therapy.**

For Stratum A, one dose de-escalation cohort (Dose Level -1) will be permitted for excessive toxicity observed at the initial (Dose Level 1) cohort. For Stratum B and Stratum C, two dose de-escalation cohorts (up to Dose Level -2) will be permitted for toxicity observed at initial cohorts.

For participants treated on Stratum A no dose escalation will proceed beyond Dose Level 3 (60 mg). For participants treated on Stratum B, no dose escalation will proceed beyond Dose Level 2 (100 mg). For participants treated on Stratum C, no dose escalation will proceed beyond Dose Level 1.

Dose Escalation Schedule			
Dose Level	Dose of Cabozantinib (XL184)*		
	Stratum A ART Regimens Including Drugs that Inhibit CYP3A4 A (mg/day)	Stratum B ART Regimens Including Drugs that Induce CYP3A4 B (mg/day)	Stratum C All Other ART Regimens C (mg/day)
Level -2	-	20	20
Level -1	20 mg every other day	40	40
Level 1	20	60	60
Level 2	40	100	-
Level 3	60	-	-

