### 5.2 Definition of Dose-Limiting Toxicity

Dose escalation decisions for cabozantinib will be made after evaluation of toxicities in the first cycle of therapy. In this trial, a dose-limiting toxicity (DLT) will be defined as any cabozantinib-related grade 3 or 4 non-hematologic toxicity during the first cycle of therapy, including grade 3 nausea and/or vomiting and grade 3 diarrhea despite prophylaxis and/or treatment or any of the following grade 4 hematologic toxicities during the first cycle of therapy: thrombocytopenia and neutropenia of any duration (with or without fever or documented infection); additionally, treatment delay of greater than 7 days during Cycle 1 due to unresolved toxicity or any dose reduction required during Cycle 1 due to a cabozantinib-related adverse event (including for intolerable cabozantinib-related grade 2 non-hematological toxicity – per Table 6-1) will be considered a DLT.

For all participants who experience a DLT or other persistent and severe toxicity, a blood sample for pharmacokinetics analysis will be requested from the participant (if feasible). The samples should be drawn as close as possible to the time of the event.

If a DLT occurs in one participant at a particular dose level, up to 3 additional participants will be added to that cohort. If a second participant experiences a DLT, the maximally tolerated dose (MTD) of the study will have been exceeded. If 2 DLTs are experienced at the first cohort, one dose level de-escalation (Dose Level -1) will be permitted according to the study schema suggested in the treatment plan.

Management and dose modifications associated with the above adverse events are outlined in [Section 6.0](#).

Dose escalation will proceed in participant cohorts within each Stratum ([Section 5.1](#)) according to the following scheme. Participants are considered evaluable for the purpose of cohort dose escalations if in the first cycle they either experience a DLT (defined above), or receive at least 80% of the planned treatment dose and are followed for one full cycle without a DLT. Participants receiving less than 80% of the treatment dose during cycle 1 without a DLT may be replaced for the purpose of safety and PK evaluation at the discretion of the study team.

Number of Participants with DLT at a Given Dose Level	Escalation Decision Rule
0 out of 3	Enter 3 participants at the next dose level.

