## 6.0 DOSING DELAYS/DOSE MODIFICATIONS

### Dose modifications for Cabozantinib (XL184)

Toxicities warranting treatment delays and dose modifications, along with supportive care guidelines, are noted below.

Stratum-based dose de-escalation of cabozantinib will be permitted for participants experiencing specified toxicity when treated at a particular dose level, as noted below; reductions will be at one-dose-level increments. In no case will dose de-escalation occur beyond the lowest specified Dose Level dose for a particular Stratum (Dose Level -1 for Stratum A; Dose Level -2 for Stratum B and Stratum C). Dose reductions are permanent. No intra-participant dose escalation will be permitted.

**NOTE: Dose modification during Cycle 1 WILL be permitted.** Participants will be permitted to continue study therapy provided no other criteria for protocol discontinuation apply ([Section 5.4](#)). **HOWEVER, treatment delay of 14 days or longer due to unresolved toxicity during Cycle 1 will require discontinuation of study treatment** ([Section 5.4](#)).

**NOTE:** If a participant experiences several adverse events and there are conflicting recommendations, the investigator should use the recommended dose adjustment that reduces the dose to the lowest level.

**NOTE:** Starting in Cycle 2, if toxicity requiring treatment delay does not resolve in less than or equal to 6 weeks, the study treatment will be discontinued. Treatment delays for other reasons may be permitted at the discretion of the Study Chairs.

Dose De-Escalation Schedule			
Dose Level	Dose of Cabozantinib (XL184)*		
	Stratum A ART Regimens Including Drugs that Inhibit CYP3A4 A (mg/day)	Stratum B ART Regimens Including Drugs that Induce CYP3A4 B (mg/day)	Stratum C All Other ART Regimens C (mg/day)
Level -2	-	20	20
Level -1	20 mg every other day	40	40
Level 1	20	60	60
Level 2	40	100	-
Level 3	60	-	-

\* Cabozantinib (XL184) must be taken whole and on an empty stomach. Participants must fast for 2 hours before and 1 hour following each dose of cabozantinib (XL184). To permit pharmacokinetic sampling studies, AM dosing is required during the first cycle of therapy.

AStratum A: Participants taking either ritonavir-boosted or cobicistat-boosted ART regimens

BStratum B: Participants taking either efavirenz or etravirine-based ART regimens.

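### Stratum B dose steps conflict (20 mg per cohort in the Synopsis, 60 then 100 mg in the tables); less clearly, so does the de-escalation depth in Strata B and C

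*Combined protocol and SAP*

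**What the plan says.** **Stratum B steps.** The Synopsis (Regimen) defines the standard dose as 60 mg, treats Stratum B at that dose, "then dose escalated by 20 mg/cohort to a maximum of 100 mg/day in a 3 + 3 design". For Stratum A the same paragraph says "Dose increases will be in 20 mg increments to a maximum of 60 mg/day". It also says that dosing is a "once daily dose continuously for 28-day cycles, according to the Protocol Schema".

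The Schema's "Dose Escalation Schedule" table, the same table in Section 5.1 and the "Dose De-Escalation Schedule" table in Section 6.0 are identical for Stratum B: Level -2 = 20, Level -1 = 40, Level 1 = 60, Level 2 = 100 mg/day. The 5.1 text caps Stratum B at Dose Level 2 and gives that level as 100 mg.

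**De-escalation.** Section 5.2 says that after two DLTs in the first cohort "one dose level de-escalation (Dose Level -1) will be permitted according to the study schema suggested in the treatment plan". It names no stratum. Section 5.1 says "For Stratum B and Stratum C, two dose de-escalation cohorts (up to Dose Level -2) will be permitted". Section 12.1 agrees with 5.1: down to Level -1 in Stratum A and to Level -2 in Strata B and C. Section 5.4 makes Level -2 the lowest dose for an individual in B and C, but does not say whether a cohort opens there.

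**Accrual.** Section 12.2 expects about 16 to 42 participants: 4 to 18 in Stratum A, 6 to 18 in B and 6 in C. It gives no derivation.

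**The concern.** The MTD is part of the primary objective (Section 1.1), and Section 12.3 has it determined separately in each stratum. In a 3+3 design the ladder and its floor decide which doses can be declared the MTD. Two ladders for one stratum therefore mean two possible sets of answers.

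The ladder also governs individual dose reductions, because Section 6.0 lowers the dose one level at a time. One level below 100 mg is a different dose on each reading.

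The depth of cohort de-escalation matters in the same way at the lower end, for Strata B and C.

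**Working it through.** **1. The Stratum B ladder**

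- Synopsis: 60, 60 + 20 = 80, 80 + 20 = 100. Three levels.
- Tables: 60, 100. Two levels, and the single step is 100 - 60 = 40 mg.
- Check on Stratum A: 20, 20 + 20 = 40, 40 + 20 = 60. This is exactly the tabulated ladder, so the Synopsis step size is accurate in A and fails only in B.

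**2. Consequences of the two ladders**

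| | Tables | Synopsis |
|---|---|---|
| Levels cleared before 100 mg opens | 60 | 60 and 80 |
| Fewest participants cleared (0 of 3 with a DLT at each level) | 3 x 1 = 3 | 3 x 2 = 6 |
| Can 80 mg be the MTD? | No | Yes |
| One level below 100 mg | 60 mg | 80 mg |

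**3. De-escalation depth in Strata B and C**

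| Section | Lowest cohort level | Lowest dose that can be the MTD |
|---|---|---|
| 5.2, as worded | Level -1 | 40 mg |
| 5.1 and 12.1 | Level -2 | 20 mg |

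In Stratum A all three sections agree on Level -1.

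**4. Can Section 12.2 decide between the readings?**

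The printed totals are the sums of the stratum figures: 4 + 6 + 6 = 16 and 18 + 18 + 6 = 42. Two simple counting rules, inferred because none is stated, reproduce the parts.

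- Minima, as 2 participants (both with a DLT) at each level from the start down to the floor in 5.1 and 12.1: A 2 x 2 = 4, B 2 x 3 = 6, C 2 x 3 = 6, total 16, as printed. With only one level down in B and C: 4 + 4 + 4 = 12.
- Maxima, as 6 per level from the start upward: A 6 x 3 = 18, B on 60/80/100 6 x 3 = 18, C 6 x 1 = 6, total 42, as printed. With 60/100 in B: 6 x 2 = 12, total 18 + 12 + 6 = 36.

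The second rule leaves out de-escalation. Following every path allowed by the 5.2 rules gives other ranges. The rules applied are: 0 of 3 escalates; 1 of 3 adds three; two or more DLTs step down; a level left at 3 is filled to 6 before it can be the MTD. Replacements and the optional expansion to 6 to 12 at the MTD are not counted.

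| Rule set | Minimum if a level may close on 2 DLTs in 2 participants | Minimum in full cohorts of 3 | Maximum |
|---|---|---|---|
| B, tables, two levels down | 6 | 9 | 24 |
| B, tables, one level down | 4 | 6 | 18 |
| B, 60/80/100, two levels down | 6 | 9 | 30 |
| B, 60/80/100, one level down | 4 | 6 | 24 |
| C, two levels down | 6 | 6 | 18 |
| C, one level down | 4 | 6 | 12 |
| A, one level down | 4 | 6 | 24 |

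Example of the 24 in the first row: 0 of 3 with a DLT at 60; six treated at 100 with two DLTs; three more at 60 with two DLTs; six at 40 with two DLTs; six at 20. That is 6 x 4 = 24.

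The printed minima therefore fit one counting rule and the printed maxima another, and the maxima are not the most that the escalation rules allow.

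**The case against.** **The Synopsis is only a summary and defers to the Schema.** Three identical tables and the 5.1 text agree with one another. Appendix V leaves escalation decisions to the Protocol Chair, the Medical Monitor and the Group Statistician. All of this stands as mitigation. A reader might infer that an 80 mg cohort is likely to be opened by mistake, and the documents do not support that. The conflict remains, though: the paragraph that cites the Schema also states a step size that the Schema contradicts, and the central decisions rest on the protocol's own rules.

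**Section 5.2 may describe only the first step down.** It deals with two DLTs in the first cohort and refers to a schema that lists Level -2, while 5.1 and 12.1 are stratum-specific and agree. This largely stands and makes the de-escalation point the weaker of the two. As worded, however, the bracketed level reads as a limit.

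**Section 12.2 settles the matter.** A reader might take its minima as proof of two levels down, or its maxima as proof of an 80 mg level. Both rest on inferred counting rules, and 12.2 gives approximate expectations. A reader might also note that 6 to 18 matches the tabulated Stratum B ladder with one level down in full cohorts of 3. That premise fails in the same sentence of 12.2: full cohorts give Stratum A a minimum of 3 x 2 = 6, not the printed 4. The 5.2 decision table, moreover, gives no denominator for two or more DLTs, so closing a level after two participants is open. No reading of 12.2 identifies the governing rule.

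**Conclusion.** The concern holds, with its two parts at different strengths.

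- **Stratum B steps: a plain contradiction in current text.** It changes the minimum cleared before 100 mg opens (3 or 6), whether 80 mg can be the MTD, and the dose one level below 100 mg (60 or 80 mg). None of these counts depends on an assumed toxicity rate.
- **De-escalation in Strata B and C: an ambiguity that reads as a contradiction.** It bears on whether 20 mg can be the MTD in those strata.
- **Section 12.2: needs checking, but is not a tie-breaker.** Full paths reach 24 in Stratum B (tabulated ladder, two levels down) and 18 in Stratum C, against printed figures of 18 and 6.

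How often the readings would lead to different MTDs cannot be sized, because the documents give no DLT rates. The path counts assume the 5.2 rules without replacements or expansion at the MTD.

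One minor wording point: after a single DLT, the 5.2 text sets three further participants as a ceiling and its table sets three as a floor. Both allow exactly three.

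**What to change.** Reconcile the Synopsis, the Schema and Sections 5.1, 5.2, 6.0 and 12.1 so that they state one Stratum B ladder and one cohort de-escalation depth per stratum. In 5.2, name the strata and say whether the sentence on de-escalation describes a first step or a limit, and align its text and table on the number added after one DLT. Then check the accrual figures in 12.2 against the reconciled rules and state how they are derived. Which ladder and which depth apply is for the sponsor to decide.

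The cost is a wording amendment, with no new data or visits. The accrual figures may need updating after the check.

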#### **5.4 Duration of Therapy**

In the absence of treatment delays due to adverse event(s), treatment may continue until one of the following criteria applies:

- Disease progression,
- Intercurrent illness that prevents further administration of treatment,
- Dose-limiting toxicity (DLT requiring discontinuation of therapy, as defined in [Section 5.2](#)). Dose reductions in the first cycle of therapy for cabozantinib-related adverse events are permitted.
- Other unacceptable adverse event(s),
- Treatment delay of 14 days or greater during Cycle 1 due to unresolved toxicity (DLT definition, [Section 5.2](#)).
- Treatment delay in subsequent cycles > 6 weeks due to toxicity (treatment delays for other reasons may be permitted at the discretion of the Study Chairs),
- Participant decides to withdraw from the study.
- General or specific changes in the participant's condition render the participant unacceptable for further treatment in the judgment of the investigator, including:
  - Necessity for treatment with other anticancer treatment prohibited by the protocol.
  - Change to a ritonavir or cobicistat-containing antiretroviral regimen for a participant enrolled on a different study arm (see [Section 5.3.1.2](#)).
  - Sexually active participants who refuse to use medically accepted barrier methods of contraception (e.g., male condom, female condom) during the course of the study and for 6 months following discontinuation of study treatment.
  - Women who become pregnant or are breastfeeding.
- Request by regulatory agencies for termination of treatment of an individual participant or all participants under the protocol.
- Significant noncompliance with the protocol schedule in the opinion of the investigator.
- The minimum dose of study treatment for Stratum A will be the Dose Level -1 dose, and the lowest dose of study treatment for Stratum B and Stratum C will be the Dose Level -2 dose. Participants who cannot tolerate the lowest Dose Level dose for the specified study Stratum will have study treatment discontinued.

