## 12.0 STATISTICAL CONSIDERATIONS

### 12.1 Study Design/Endpoints

This is a phase I, dose escalation study of cabozantinib for advanced solid tumors in persons with HIV infection. The primary endpoint of the study is the safety and tolerability of single agent cabozantinib and to determine the maximal tolerated dose (MTD) in this participant population. The study will be a standard phase I dose escalation trial with a 3+3 design. The study agent will be administered continuously in 28 day cycles.

Participants will be stratified based on HAART with the currently recommended dosing regimen. Participants on ritonavir or cobicistat (potent CYP3A4 inhibitor)-containing HAART will be on Stratum A; participants on efavirenz or etravirine (CYP3A4 inducer)-containing HAART will be on Stratum B, and all other participants (including those without antiretroviral therapy) will be on Stratum C. Dose escalation and MTD determination will be done for each stratum individually. Participants are considered evaluable for the purpose of cohort dose escalations if in the first cycle they either experience a dose-limiting toxicity (DLT) (see below), or receive at least 80% of the planned treatment dose and are followed for one full cycle without a DLT. Participants receiving less than 80% of the treatment dose during cycle 1 without a DLT may be replaced for the purpose of safety and PK evaluation at the discretion of the study team.

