Dose escalation decisions for cabozantinib will be made after evaluation of toxicities in the first cycle of therapy. In this trial, a dose-limiting toxicity (DLT) will be defined as any cabozantinib-related grade 3 or 4 non-hematologic toxicity during the first cycle of therapy, including grade 3 nausea and/or vomiting and grade 3 diarrhea despite prophylaxis and/or treatment or any of the following grade 4 hematologic toxicities during the first cycle of therapy: thrombocytopenia and neutropenia of any duration (with or without fever or documented infection); additionally, treatment delay of greater than 7 days during Cycle 1 due to unresolved toxicity or any dose reduction required during Cycle 1 due to a cabozantinib-related adverse event will be considered a DLT. If a DLT occurs in one participant at a particular dose level, up to 3 additional participants will be added to that cohort. If a second participant experiences a DLT, the maximally tolerated dose (MTD) of the study will have been exceeded. If 2 DLTs are experienced at the first cohort, dose de-escalation cohorts (up to Dose Level -1 for Stratum A; up to Dose Level -2 in Stratum B and Stratum C) will be permitted according to the study schema suggested in the treatment plan.

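### The definition of dose-limiting toxicity stands in two incompatible versions, so a Cycle 1 toxicity delay of 8 to 13 days can count as a DLT or drop out of the count

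*Combined protocol and SAP*

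**What the plan says.** Three places state what a DLT is, and a fourth refers to the definition.

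- **Synopsis, Regimen.** A delay counts at "treatment delay of 14 days or greater during Cycle 1 due to unresolved toxicity". Grade 4 neutropenia counts only as "neutropenia of more than 5 days duration, and neutropenia of any duration with fever or documented infection".
- **Section 5.2.** The grade 4 hematologic criteria and the delay criterion read "thrombocytopenia and neutropenia of any duration (with or without fever or documented infection); additionally, treatment delay of greater than 7 days during Cycle 1".
- **Section 12.1.** The neutropenia wording is the same as in 5.2, and the delay criterion is "treatment delay of greater than 7 days during Cycle 1 due to unresolved toxicity or any dose reduction required during Cycle 1".
- **Section 5.4.** Among the reasons to stop treatment is "Treatment delay of 14 days or greater during Cycle 1 due to unresolved toxicity (DLT definition", with Section 5.2 named as the source. Section 5.2 has no 14-day threshold.

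All versions agree that a related grade 3 or 4 non-hematologic event is a DLT. They also agree on required reductions; in the Synopsis wording, any "dose reduction required during Cycle 1 due to a cabozantinib-related adverse event will be considered a DLT".

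The evaluability rule is in Sections 5.2 and 12.1. A participant without a DLT is evaluable only if they "receive at least 80% of the planned treatment dose and are followed for one full cycle without a DLT". Otherwise the replacement rule applies: "Participants receiving less than 80% of the treatment dose during cycle 1 without a DLT may be replaced", at the study team's discretion.

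Section 6.0 also uses 14 days, but only as a rule for discontinuing treatment. That can coexist with a shorter DLT threshold and is not part of the conflict.

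**The concern.** The primary objective includes finding the maximum tolerated dose (MTD), and Section 12.1 has this done separately in each stratum. The only data entering the 3+3 rules are DLT counts among three to six participants, so reclassifying one participant can change the decision. Appendix V bases escalation on the protocol's rules, and here the protocol holds two sets.

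The two versions do more than shift a cut-off. Under 5.2 and 12.1, a participant in the disputed window adds a DLT. Under the Synopsis threshold, the same participant has no DLT, has taken too little drug to be evaluable, and may be replaced. The toxicity that caused the hold is then not counted at all. The discrepancy always runs in one direction: the Synopsis version makes it easier to escalate or to declare a dose tolerated.

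The conflict also matters where no higher dose exists (Stratum C, and the top levels of Strata A and B). There the same count decides whether the dose is accepted.

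**Working it through.** The plan gives no DLT rate or operating characteristics, so there is no figure of its own to reproduce on this point. Its expected enrolment of 16 to 42 adds up (4+6+6 = 16; 18+18+6 = 42) and does not bear on the question.

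**1. Who is affected.** Related grade 3–4 non-hematologic events and required Cycle 1 reductions are DLTs in every version. The delay threshold decides alone only when neither applies. Table 6-1 allows such a case: an intolerable grade 2 event may be held and then resumed at the same dose at the investigator's discretion.

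**2. Evaluability after a hold.** Inputs are once-daily dosing, a 28-day cycle and the 80% rule. Assumptions are that the hold lies wholly within Cycle 1, held doses are not made up, and a delay does not lengthen the cycle. Fraction taken = (28 − days held)/28; 80% requires 23 doses.

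| Days held | Doses taken | Share |
|---|---|---|
| 5 | 23/28 | 82.1% |
| 8 | 20/28 | 71.4% |
| 10 | 18/28 | 64.3% |
| 13 | 15/28 | 53.6% |

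Every hold of 8 to 13 days fails the 80% rule. Holds of 6 and 7 days (78.6% and 75.0%) also fail it and are not delay DLTs in any version. That gap is separate from the contradiction.

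**3. One cohort, two decisions.** Suppose one of three participants has a related grade 3 non-hematologic event, one has a 10-day hold for intolerable grade 2 toxicity and resumes at the same dose, and one has no event. Under 5.2 and 12.1 there are 2 DLTs and escalation stops. Under the Synopsis there is 1 DLT, the held participant may be replaced, and enrolment at that level continues.

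**4. Size, for illustration only.** Let p be the rate of DLTs under the Synopsis and d the rate of disputed participants. Neither is in the documents; both are assumed. The DLT probability per evaluable participant is:

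- under 5.2 and 12.1: q = p + d
- under the Synopsis with replacement: q = p/(1 − d)

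P(escalate) = (1 − q)³ + 3q(1 − q)⁵.

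| p | d | q, Synopsis | P(escalate) | q, 5.2/12.1 | P(escalate) | Difference |
|---|---|---|---|---|---|---|
| 0.20 | 0.02 | 0.2041 | 0.700 | 0.22 | 0.665 | 0.035 |
| 0.20 | 0.05 | 0.2105 | 0.686 | 0.25 | 0.600 | 0.086 |
| 0.20 | 0.10 | 0.2222 | 0.660 | 0.30 | 0.494 | 0.166 |
| 0.15 | 0.10 | 0.1667 | 0.780 | 0.25 | 0.600 | 0.180 |

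Where there is no higher level, P(at most 1 DLT in 6) = (1 − q)⁶ + 6q(1 − q)⁵. With p = 0.20 this is 0.630 (Synopsis) against 0.534 at d = 0.05, and 0.601 against 0.420 at d = 0.10.

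**5. Neutropenia.** This conflict is narrower. Table 6-2 calls for resumption one level lower after related grade 4 neutropenia, and a required Cycle 1 reduction is a DLT in every version. The difference remains only if the reduction falls after Cycle 1, dosing is not resumed, or the event is judged unrelated.

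**The case against.** The strongest reply is that the operative rule can be identified. Section 5.1 sends escalation to the scheme in Section 5.2, whose title is the DLT definition, and 12.1 uses the same thresholds. Under Appendix V, the Protocol Chair, Medical Monitor and Group Statistician decide centrally whether the criteria are met. The Synopsis would then be a stale paragraph. This lowers the risk of a wrong decision, but it is not a precedence rule, and none was found. The Synopsis would still be wrong, and so would a cross-reference in the body of the protocol.

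Section 5.4 can be read more kindly: any delay of 14 days also exceeds 7 days, so it is a DLT under 5.2 as well as a reason to stop. That reading is possible, but the bullet labels the 14-day figure as Section 5.2's definition, which it is not.

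The replacement mechanism also combines two texts, since the 80% rule is absent from the Synopsis, and replacement is discretionary. Both points are true. However, the 80% rule is the only evaluability rule in the protocol. If the participant were instead kept as a non-DLT, the gap would widen: with p = 0.20, P(escalate) is 0.709 under the Synopsis, against 0.600 (d = 0.05) or 0.494 (d = 0.10).

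Finally, many management rules pair a hold with a dose reduction, so the disputed group may be small. That stands, and it limits the likely size of the effect.

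**Conclusion.** The concern holds. The current text classifies the same participant differently by section, on the rule that determines the primary endpoint. The contradiction rests on the wording alone.

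Its numerical effect is uncertain. In the assumed scenarios the Synopsis version raises the chance of escalating by 3.5 to 18.0 percentage points, for disputed shares of 2 to 10 points. The lower end may be nearer the truth, because most serious Cycle 1 toxicity is a DLT in both versions. The 80% result assumes a fixed 28-day cycle with held doses not made up. In cohorts of three to six, a single disputed participant is enough to reverse a decision, so this should be corrected even if such cases are rare.

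**What to change.** - State one identical DLT definition, covering both delay and grade 4 neutropenia, in the Synopsis, Section 5.2 and Section 12.1. Which threshold applies is for the sponsor; the passages must be reconciled.
- Correct the Section 5.4 bullet so that it either matches that definition or is labelled only as a discontinuation rule, without citing 5.2 for a 14-day DLT threshold.
- Recheck completed cohorts for Cycle 1 toxicity delays of 8 to 13 days and for short grade 4 neutropenia. Include participants replaced as non-evaluable, and confirm that each escalation or MTD decision stands under the reconciled definition.

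The cost is a wording amendment and a review of data already collected. No extra participants or procedures are needed for the correction itself.
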